1.2 Preventing DR Onset and Worsening

At this time, the primary method of slowing DR onset and worsening remains that of strict glycemic control and blood pressure control. Results from the Early Treatment Diabetic Retinopathy Study (ETDRS) revealed that better glycemic control inhibits DR worsening among all age groups, type 1 and type 2 diabetes, and all stages of retinopathy.⁶ The United Kingdom Prospective Diabetes Study (UKPDS) and the Action to Control Cardiovascular Risk in Diabetes (ACCORD) Study demonstrated that improved blood glucose control can reduce the risk of developing DR in patients with type 2 diabetes, with the UKPDS additionally showing the benefit of improved blood pressure control.^{7,8} The Diabetes Control and Complications Trial (DCCT) found that intensive therapy, aimed at keeping glycemic levels as close to normal range values as possible, reduced the risk of any DR developing by 76% (95% confidence interval (CI):62% to 85%) among patients with no DR at baseline and slowed the worsening of DR by 54% (95% CI: 39% to 66%) among patients with mild DR at baseline.⁹ The benefits of intensive treatment were sustained for approximately 4 years after the period of intensive glycemic control with a 75% ($P<0.001$) risk reduction in the worsening of DR.¹⁰ This beneficial effect in fact persisted for even as long as 18 and 25 years later in this cohort of study participants with type 1 diabetes.^{11,12} This beneficial effect also persisted in type 2 diabetes.^{13,14}

Despite improvements in systemic glycemic control,¹⁵ there continues to be a substantial proportion of diabetic patients who develop DR and its associated sequelae. In 2005–2008, 28.5% (4.2 million) of Americans with diabetes aged 40 years or older had DR, and of this group, 655,000 individuals had advanced DR that could lead to severe vision loss.¹⁶ Approximately 40-60% of the Wisconsin Epidemiologic Study Diabetic Retinopathy (WESDR) cohort, whose onset of diabetes occurred between 1922 and 1980, developed proliferative diabetic retinopathy (PDR) over time, with rates of visual impairment (vision of 20/40 or less in the better seeing eye) ranging from approximately 5% to 20%.¹⁵

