5.5 Contact Information Provided to the DRCR.net Coordinating Center

The Coordinating Center will be provided with contact information for each study participant. Permission to obtain such information will be included in the Informed Consent Form from the PROMINENT study and from the PROMINENT-Eye study. The contact information will be maintained in a secure database and will be maintained separately from the study data.

Contact from the Coordinating Center may be made for each study participant in the first month after enrollment, and approximately every six months thereafter. Additional contacts from the

547 Coordinating Center will be made if necessary to facilitate the scheduling of the study participant
548 for follow-up visits. A participant-oriented newsletter may be sent once a year. A study logo item
549 may be sent once a year.

550
551 Study participants may be provided with a summary of the study results in a newsletter format after
552 completion of the study by all participants.

553
554 **5.6 Subject Reimbursement**
555 The Coordinating Center will provide each study participant with a \$50 merchandise or money card
556 per completed protocol visit. Additional travel expenses may be paid in cases for participants with
557 higher expenses.

558
559
560
561
562
563
564
565
566
567
568
569
570
571
572
573
574
575
576
577
578
579
580
581
582
583
584
585
586

STATISTICAL CONSIDERATIONS

The approach to sample size and statistical analysis is summarized below. A detailed statistical analysis plan will be written and finalized prior to the completion of the study.

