 611 15% attrition over 4 years, also assumed to follow an exponential distribution.

612

Table 3. Required Number of Participants for Primary Analysis

Hazard Ratio	Placebo Event Rate				
	16%	14%	12%	10%	8%
0.30	270	310	364	438	552
0.40	398	458	536	646	812
0.50	618	710	832	1000	1256

613

614

615
616 The projected 4-year outcome rates of 5% in the pema fibrate group and 12% in the placebo group
617 yield a hazard ratio of approximately 0.4, resulting in a required sample size of 536 participants.
618

619 Assuming 600 participants are enrolled of whom 15% are lost to follow up over 4 years, the
620 detectable hazard ratio with 80% power is 0.49 for a placebo event rate of 16% to 0.32 for a placebo
621 event rate of 8%. In other words, the study is powered for a reduction in the rate of diabetic
622 retinopathy worsening by 1/2 to 2/3, depending on the event rate in the placebo group. The placebo
623 event rate could be higher than 16% because the 12% estimate from ACCORD accounts for events
624 due only to progression of retinopathy on photographs and does not include treatment-related and
625 DME-related events, which are other components of the composite outcome. There are no existing
626 data on which to base estimates for rates of these outcomes. In the event that the outcome rates in
627 the placebo group are higher than projected, the study will be powered to detect smaller reductions
628 in the hazard of diabetic retinopathy worsening. Therefore, the estimates given here are
629 conservative.
630

631 **6.3 Primary Analysis Plan**

632 **6.3.1 Principles for Analysis**

633 The primary treatment group comparison will be based on the hazard ratio from a Cox proportional
634 hazards regression model that adjusts for the baseline person-level retinopathy, which accounts for
635 the retinopathy level in the non-study eye of unilateral participants (see **Table 1**). The primary
636 analysis is an intention-to-treat analysis. Data from participants who are not observed to meet
637 outcome criteria and who are lost to follow up will be censored at the time of the last completed
638 visit. All model assumptions, including proportional hazards, will be verified. If model
639 assumptions are not reasonably satisfied, alternative approaches will be explored.
640

641 **6.3.2 Confounding**

642 Imbalances between groups in important covariates are not expected to be of sufficient magnitude

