643 to produce confounding. However, the presence of confounding will be evaluated in regression
644 models by including factors potentially associated with the outcome for which there is an imbalance
645 between groups.
646

647 **6.3.3 Per Protocol Analyses**

648 Per protocol analyses mimicking the primary intention-to-treat analyses will be performed on the
649 following cohorts:
650

- 651 • Participants with no major protocol deviations as defined by the PROMINENT trial.
 - 652 • Participants with $\geq 80\%$ compliance during the treatment period as defined by the
653 PROMINENT trial.
- 654

655 **6.3.4 Sensitivity Analyses**

656 The following sensitivity analyses will be conducted:
657

- 658 • Repeat the primary analysis while censoring data from participants who receive treatment
659 for DME when the OCT central subfield thickness in the treated eye did not meet the
660 outcome criteria for DME with vision loss when the treatment was given. Participants who
661 do not have an OCT scan from the visit at which treatment is given also will be censored in
662 this analysis.
663

664 **6.3.5 Subgroup Analyses**

665 The treatment effect in subgroups defined by baseline factors will be assessed in pre-planned
666 subgroup analyses. These analyses will be conducted to determine whether the treatment effect in
667 any subgroup differs from the overall treatment effect. The study is not expected to have sufficient
668 statistical power for definitive conclusions in subgroups and statistical power will be low to
669 formally test for the presence of subgroup effects. Interpretation of subgroup analyses will depend
670 on whether the overall analysis demonstrates a significant treatment effect. In the absence of a
671 significant treatment effect in the primary analysis, assessment of subgroups will be considered
672 exploratory and used to suggest hypotheses for further investigation in future studies.

673
674 The general approach for these analyses will be to add an interaction term for the subgroup factor
675 by treatment group into the proportional hazards model used for the primary analysis.

676
677 The planned subgroups for analyses are as follows:

- 678 • Baseline person-level retinopathy level: Steps 2-4, Steps 5-6, Steps 7-9, and Steps 10-11

679
680 Statistical analyses will only be conducted for a subgroup if there are at least 20 participants in each

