681 treatment group for that subgroup. The above subgroups are considered those of primary interest
682 for which a rationale for a subgroup effect is hypothesized. The hypothesized mechanism and
683 direction of effect are listed in the table below.

Factor	Hypothesized direction/mechanism of association
Retinopathy Level	Participants with more severe retinopathy have higher risk for retinopathy worsening and may have disease that is too advanced for the treatment to work. Therefore, it is possible that the treatment effect is greater in eyes with less severe disease.

684
685
686 The following baseline subgroup factors also will be evaluated in exploratory analyses:

- 687 • Prior DME treatment: yes vs. no
- 688 • Age: < 65 vs. ≥ 65
- 689 • HbA1c: < 7.5% vs. ≥ 7.5%
- 690 • Sex
- 691 • Race/Ethnicity
- 692 • Hyperlipidemia status: ≥ HDL (high-density lipoprotein) median of the sample cohort and ≥
693 TG (triglyceride) median; ≥ HDL median and < TG median; < HDL median and ≥ TG
694 median; < HDL median and < TG median
- 695 • Number of study eyes: 1 vs. 2

696
697
698 There is no known mechanism supporting an interaction of these effects with treatment group. If a
699 significant subgroup effect for any of these factors is found, it will be interpreted as hypothesis
700 generating only and in need of confirmation from further studies. In particular, there are no data to
701 suggest that the treatment effect will vary by sex or race/ethnicity, although both of these factors
702 will be evaluated.

703
704 For all analyses, P-values will be computed for factors based on continuous or ordinal data when
705 available in addition to the categorizations listed above.

706

707 **6.4 Secondary Outcomes and Safety Outcomes for Treatment Group Comparison**

708 Secondary outcomes will be compared at the 2-year and 4-year visits with the exception of time-to-
709 event outcomes in which the hazard rates will be compared over 4 years only. Safety outcomes
710 collected as part of this ancillary study will be compared at 4 years only. To control for potential
711 correlations arising from participants with two study eyes, eye-level outcomes will be compared
712 using linear mixed models (continuous outcomes), logistic regression using generalized estimating
713 equations (binary outcomes), or Cox proportional hazards regression with a robust sandwich
714 estimate of the covariance matrix (time-to-event outcomes).³³ Participant-level outcomes will be

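### The primary Cox model omits baseline HbA1c, and section 6.3.2 brings in other covariates only on observed imbalance; fixing covariates in advance would be a modest improvement

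*Combined protocol and SAP*

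**What the plan says.** - **Primary model (6.3.1).** The treatment comparison is the hazard ratio from a Cox proportional "hazards regression model that adjusts for the baseline person-level retinopathy, which accounts for" the non-study eye of unilateral participants. Baseline person-level retinopathy is the only covariate.
- **Other covariates (6.3.2).** The plan states: "Imbalances between groups in important covariates are not expected to be of sufficient magnitude" to cause confounding. Confounding will still be examined in regression "models by including factors potentially associated with the outcome for which there is an imbalance" between the arms. There is no covariate list, no threshold for imbalance, and no statement of how to read a result that differs from the primary one.
- **Glycemic control (1.2).** The background says that "better glycemic control inhibits DR worsening among all age groups, type 1 and type 2 diabetes, and all stages of retinopathy". It names strict glycemic and blood pressure control as the main way to slow onset and worsening.
- **HbA1c in the analysis (6.3.5).** It appears once, among the exploratory baseline subgroup factors, as "HbA1c: < 7.5% vs. ≥ 7.5" percent. The same section also calls for P-values on the continuous scale where such data exist. Of these factors the plan says: "There is no known mechanism supporting an interaction of these effects with treatment group".
- **What is still to come (opening of section 6).** "A detailed statistical analysis plan will be written and finalized prior to the completion of the study".

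**The concern.** The plan intends to use baseline HbA1c for effect modification, where it claims no rationale. It does not use it for prognosis, which is where its own background points.

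The route in 6.3.2 is the weaker part of the plan. Choosing covariates because the arms differ means that both the list and the trigger are settled after data by arm have been seen. If the arms look alike, no adjustment is made and the efficiency from a prognostic covariate is lost. If they differ, the adjusted result is post hoc, and the plan gives no guidance on reading it beside the primary one.

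At stake are a little power in a study with few events, and the credibility of any adjusted result shown next to the primary one.

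**Working it through.** **1. Reproduce the plan's sample size.** Inputs from section 6.2: two-sided 5%, 80% power, log-rank test, 12% placebo rate at 4 years, HR 0.40, 15% attrition, exponential events and attrition. Allocation 1:1 is assumed, because the documents do not state it.

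- HR from the projected rates: ln(0.95)/ln(0.88) = 0.401, stated as about 0.4.
- Log-rank size by numerical integration (Lakatos type): N = (z₀.₉₇₅ + z₀.₈₀)² × Σ D·θ/(1+θ)² ÷ {Σ D·[φθ/(1+φθ) − θ/(1+θ)]}². Here D is the expected events per participant in each small interval, θ the ratio of numbers at risk, and φ the hazard ratio. Result: **536**, against the stated 536. All 15 cells of Table 3 agree within 2 participants.
- Detectable HR with 600 enrolled: 0.493 at a 16% placebo rate and 0.323 at 8%, stated as 0.49 and 0.32.

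The plan's figures stand.

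**2. Expected events.**

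- 12% rate, HR 0.40: about 42 at N = 536 and about 47 at N = 600.
- 16% rate, HR 0.49: about 67 at N = 600.

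**3. Effect of adding one HbA1c-like covariate.** The documents give no association between HbA1c and the outcome, so its strength is assumed: HR per SD of 1.25, 1.5 and 2.0. Cox models with and without a standard normal covariate were simulated with 1,500 replicates per row. The baseline hazard was set to give the stated placebo rate.

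| N, placebo rate, HR | HR per SD | Power without | Power with | Gain (points) |
|---|---|---|---|---|
| 536, 12%, 0.40 | 1.25 | 80.7% | 81.1% | 0.5 |
| 536, 12%, 0.40 | 1.5 | 79.9% | 80.3% | 0.3 |
| 536, 12%, 0.40 | 2.0 | 77.9% | 80.1% | 2.2 |
| 600, 16%, 0.49 | 1.25 | 79.1% | 79.2% | 0.1 |
| 600, 16%, 0.49 | 1.5 | 78.8% | 79.6% | 0.8 |
| 600, 16%, 0.49 | 2.0 | 78.7% | 81.6% | 2.9 |

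Gains were taken before rounding. The Monte Carlo SE of each power figure is √(0.8 × 0.2/1500) ≈ 1.0 point; it is smaller for the gains, because both models were fitted to the same data. Part of the gain reflects attenuation when the covariate is left out. At HR per SD 2.0 the median estimated HR is 0.413 without it and 0.404 with it, for a true value of 0.40.

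**4. Type I error.** Under no effect (N = 600, 2,000 replicates), for HR per SD 1.5 and 2.0, the rejection rate is 4.9% and 4.3% without the covariate, and 5.1% and 4.8% with it. Leaving HbA1c out does not inflate alpha.

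**5. Size of a chance imbalance.** With 300 per arm, the SE of the difference in means of a standardized covariate is √(4/600) = 0.0816. A 1-SE imbalance moves the log HR by ln(HR per SD) × 0.0816:

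- HR per SD 1.3: 0.262 × 0.0816 = 0.021, about 2%
- HR per SD 1.6: 0.470 × 0.0816 = 0.038, about 4%
- HR per SD 2.0: 0.693 × 0.0816 = 0.057, about 6%

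A 2-SE imbalance gives about 4% to 12%. For scale, 47 events split roughly 33 and 14 give an SE of the log HR of √(1/33 + 1/14) ≈ 0.32. A 1-SE imbalance is therefore 0.021/0.32 ≈ 7% to 0.057/0.32 ≈ 18% of one standard error.

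**The case against.** The strongest reply is that the primary analysis is already pre-specified and valid, and that it adjusts for the one factor section 6 explicitly ties to higher risk of worsening, baseline retinopathy level (6.3.5). The gain from HbA1c is small, and random imbalance is already reflected in the confidence interval. All of this is correct, and it limits the point to efficiency and pre-specification.

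Four stronger readings are tempting, and the documents do not support them.

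- *A reader might infer that the protocol calls baseline HbA1c prognostic.* It does not. Section 1.2 reports effects of glycemic control. A prognostic role for the baseline value is a fair inference, and no more. Section 1.2 gives blood pressure control similar standing.
- *A reader might infer that 6.3.2 can change the primary result.* It describes a check for confounding. The primary estimate remains the one named in 6.3.1. Nor is HbA1c shut out of every model unless imbalanced, since 6.3.5 puts it in an exploratory interaction model regardless of balance.
- *A reader might infer that the omission biases the test.* Step 4 shows no inflation of type I error.
- *A reader might infer that balance is in doubt because enrolment may follow parent randomization by up to 3 months.* The documents give no reason why enrolment would differ by arm, and adding HbA1c alone would not cure such a difference.

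It is also fair to say that the detailed SAP could settle the matter. But nothing in section 6 defers the choice of covariates to it, whereas section 6.4 does defer missing secondary data. Until the SAP says otherwise, 6.3.2 is the stated rule. Finally, HbA1c is not in the eye-study visit schedule (section 1.8 E), so it presumably comes from the parent trial, and its completeness is not stated.

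**Conclusion.** The point holds as an improvement in efficiency and pre-specification. The primary model uses baseline retinopathy alone, although the plan's own background and its subgroup list make HbA1c an obvious candidate. The rule in 6.3.2 selects covariates after data by arm are seen. It leaves the primary estimate and its type I error intact.

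The expected gain is about 0 to 3 power points for an HR per SD of 1.25 to 2.0, and below 1 point at 1.5 or less. This rests on assumed covariate strength, assumed 1:1 allocation, and a simulation without the retinopathy covariate and without visit-based detection of events. Correlation between HbA1c and baseline retinopathy would shrink the gain. No stated figure is in error: Table 3 and the detectable hazard ratios are reproduced.

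**What to change.** Before unblinding:

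1. In 6.3.1, and in the detailed SAP, add baseline HbA1c as a continuous covariate in the primary Cox model beside baseline person-level retinopathy. Name the parent-trial measurement to be used, its functional form, and a simple rule for missing values that ignores treatment arm.
2. In 6.3.2, replace the imbalance trigger with one supportive model. Its covariates should be listed in advance, with a stated prognostic reason for each, and it should be fitted whether or not the arms differ. State that the 6.3.1 model remains primary. The documents give no prognostic evidence for most of the exploratory subgroup factors, so the study team must justify the list.

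The cost is SAP wording, one extra parameter in the primary model against about 42 to 67 events, and the handling of any missing HbA1c. No new eye-study assessment is needed if the parent trial supplies the value.

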7.1 Case Report Forms

The key study data are collected through a combination of electronic case report forms (CRFs) and grading of retinal images.

When data are directly collected in electronic case report forms, this will be considered the source data. Each participating site will maintain appropriate medical and research records for this trial, in compliance with ICH E6 and regulatory and institutional requirements for the protection of confidentiality of participants.

7.2 Study Records Retention

Study documents should be retained by the investigator for the latest of 3 years following the end of the current DRCR.net grant, 2 years after the last approval of a marketing application, and until there are no pending or contemplated marketing applications, or until at least 2 years have elapsed since the formal discontinuation of clinical development of the investigational product. These documents should be retained for a longer period, however, if required by local regulations. No records will be destroyed without the written consent of the Jaeb Center for Health Research. It is the responsibility of the sponsor to inform the investigator when these documents no longer need to be retained.

7.3 Quality Assurance and Monitoring

Designated personnel from the JCHR Coordinating Center will be responsible for maintaining quality assurance and quality control systems to ensure that the clinical portion of the trial is conducted and data are generated, documented and reported in compliance with the protocol, Good Clinical Practice (GCP) and the applicable regulatory requirements.

A risk-based monitoring plan will be developed and revised as needed during the course of the study, consistent with the FDA “Guidance for Industry Oversight of Clinical Investigations — A Risk-Based Approach to Monitoring” (August 2013).

The data of most importance for monitoring at the site are participant eligibility and image outcome data. Therefore, the risk-based monitoring plan will focus on these areas. As much as possible, remote monitoring will be performed in real-time with on-site monitoring performed to evaluate the verity and completeness of the key site data when possible. Elements of the risk-based monitoring will include:

- Qualification assessment, training, and certification for sites and site personnel
- Oversight of Institutional Review Board (IRB) coverage and informed consent procedures
- Central (remote) data monitoring: validation of data entry, data edits/audit trail, protocol review of entered data and edits, statistical monitoring, study closeout
- On-site monitoring (site visits): source data verification, site visit report
- Communications with site staff
- Patient retention and visit completion
- Quality control reports
- Management of noncompliance
- Documenting monitoring activities
- Adverse event reporting and monitoring

845
846 JCHR Coordinating Center representatives or their designees may visit the study facilities at any
847 time in order to maintain current and personal knowledge of the study through review of the
848 records, comparison with source documents, observation and discussion of the conduct and progress
849 of the study.

850
851 **7.4 Protocol Deviations**

852 A protocol deviation is any noncompliance with the clinical trial protocol, GCP, or procedure
853 requirements. The noncompliance may be either on the part of the participant, the investigator, or
854 the study site staff. As a result of deviations, corrective actions are to be developed by the site and
855 implemented promptly.

856
857 The site principal investigator/study staff is responsible for knowing and adhering to their IRB
858 requirements. Further details about the handling of protocol deviations will be included in the
859 monitoring plan.

ETHICS/PROTECTION OF HUMAN PARTICIPANTS

860
861
862
863
864
865
866
867
868
869
870
871
872
873
874
875
876
877
878
879
880
881
882
883
884
885
886
887
888
889
890
891
892
893
894
895
896
897
898
899
900
901
902
903
904
905
906
907
908

